**Figure 1: Study Schematic (Part A)**

**3.1.2. Part B**

Part B will comprise a multiple-dose, single-period, sequential-cohort study. Potential subjects will be screened to assess their eligibility to enter the study within 28 days prior to initial study drug administration.

The total duration of study participation for each subject (from Screening through Safety Follow-up visit) is planned to be no more than 10 weeks but may be increased to a maximum of 12 weeks if the Additional Follow-up visit is delayed based on findings from the ongoing review of data by the DMC.

[REDACTED]

[REDACTED]

[figure not shown]
All subjects will return for a Safety Follow-up visit approximately 7 days after their last dose (Day 29 [+3]) and an Additional Follow-up visit approximately 14 days after the last dose (Day 36 [ $\pm$ 3]). The timing of the Additional Follow-up visit for a cohort may be changed to a maximum of approximately 28 days after the last dose (Day 50 [ $\pm$ 3]), based on emerging safety data.

In each of Cohorts B1 to B3, 4 subjects will receive TRK-250 and 2 subjects will receive placebo. Doses will be administered on the morning of Days 1, 8, 15, and 22 in accordance with a randomization schedule. Each subject will receive 4 once-weekly doses of TRK-250 or placebo during the study. [REDACTED]

[REDACTED]

- Cohort B1: 10 mg
- Cohort B2: 30 mg
- Cohort B3: 60 mg

[REDACTED] shown in [Figure 2](#).

**Figure 2: Study Schematic (Part B)**

A Schedule of Assessments is presented in [Appendix 5](#).

### 3.2. Study Start and End of Study Definitions

The start of the study is defined as the date the first enrolled subject signs an Informed Consent Form (ICF). The point of randomization occurs at the time of subject number allocation. The end of the study is defined as the date of the last subject's last protocol-specified assessment, whether scheduled or unscheduled.

### 3.3. Additional Cohorts

Following review of the safety and tolerability data from the planned dose cohorts, the DMC may recommend additional dose cohorts to be added to the study. Up to 3 further cohorts of at least 4 subjects [REDACTED] may be included in Part A, and up to 3 further cohorts of at least 6 subjects [REDACTED] may be included in Part B. If the dose escalation stopping criteria have not been met, the doses administered in the additional cohorts may exceed the proposed highest doses shown in [Table 4](#); [REDACTED]

The Sponsor is responsible for making the final decision whether to add any additional cohorts if recommended by the DMC. The decision will be documented in the Trial Master File (TMF), and the Institutional Review Board (IRB) will be notified of the changes.

### 3.4. Discussion of Study Design, Including the Choice of Control Groups

For both parts of the study, a sequential-cohort, ascending-dose design has been chosen for safety reasons because TRK-250 is in the early stages of clinical development, with Part A of

the study being the first time it will be administered to humans. Inhaled doses have been chosen for both parts of the study since this is the intended clinical route of administration.

[REDACTED]

[REDACTED]

This study will be double blind and placebo controlled to avoid bias in the collection and evaluation of data. Placebo has been chosen as the control treatment to assess whether any observed effects are treatment related or simply reflect the study conditions.

[REDACTED]

[REDACTED]

**3.4.1. Dose Interval**

[REDACTED]

- [REDACTED]

- [REDACTED]

[REDACTED]

[REDACTED]

[REDACTED]

**3.5. Selection of Doses in the Study**

[REDACTED]

[REDACTED]

[REDACTED]

[REDACTED]

[REDACTED]

[REDACTED]

[REDACTED]

[REDACTED]

[REDACTED]

[REDACTED]

[REDACTED]

The proposed IMP dose levels for Parts A and B are shown in [Table 4](#).

**Table 4: Proposed IMP Dose Levels for Parts A and B**

Study Part	Cohort	Treatment
Part A	A1	2 mg TRK-250 or placebo
	A2	10 mg TRK-250 or placebo
	A3	30 mg TRK-250 or placebo
	A4	60 mg TRK-250 or placebo
	Optional Cohorts A5, A6, and A7	XX mg TRK-250 or placebo
Part B	B1	10 mg TRK-250 or placebo Q1W
	B2	30 mg TRK-250 or placebo Q1W
	B3	60 mg TRK-250 or placebo Q1W
	Optional Cohorts B4, B5, and B6	XX mg TRK-250 or placebo Q1W

Abbreviations: IMP = investigational medicinal product; Q1W = once weekly.

For Part B of the study, dose levels, dosing frequency, and dosing duration will be decided, in consultation with the Sponsor, on the basis of data from Part A of the study. The weekly dose of TRK-250 administered during this part of the study will not exceed the maximum well-tolerated dose level studied in Part A.

[REDACTED]

[REDACTED]

Details of all doses administered in Parts A and B of the study will be documented in the TMF.

[REDACTED]

[REDACTED]

[REDACTED]

[REDACTED]

[REDACTED]

[REDACTED]

[REDACTED]

[REDACTED]

[REDACTED]

[REDACTED]

[REDACTED]

| [REDACTED]

| [REDACTED]

[REDACTED]

[REDACTED]

[REDACTED]

[REDACTED]

| [REDACTED]

| [REDACTED]

| [REDACTED]

| [REDACTED]

| [REDACTED]

| [REDACTED]

| [REDACTED]

[REDACTED]

[REDACTED]

[REDACTED]

[REDACTED]

[REDACTED]

[REDACTED]

[REDACTED]

[REDACTED]

[REDACTED]

[REDACTED]

[REDACTED]

[REDACTED]

[REDACTED]

[REDACTED]

[REDACTED]

[REDACTED]

[REDACTED]

[REDACTED]

- | [REDACTED]
- | [REDACTED]
- | [REDACTED]
- | [REDACTED]

[REDACTED]

- | [REDACTED]
- | [REDACTED]
- | [REDACTED]
  - | [REDACTED]
  - | [REDACTED]
  - | [REDACTED]

[REDACTED]

#### 4. SELECTION OF STUDY POPULATION

##### 4.1. Inclusion Criteria

Subjects must satisfy all of the following criteria, at the Screening visit unless otherwise stated:

1. Able to comprehend and willing to sign an ICF and to abide by the study restrictions.
2. Male or female between 40 and 80 years of age, inclusive, at Screening.
  - a. Women of childbearing potential (WCBP) and all male subjects will agree to use contraception (refer to [Section 6.5](#)) throughout enrollment (ie, from signing the ICF to the last protocol-specified assessment, whether scheduled or unscheduled).
3. Clinical, radiographic, and (when available) histologic features consistent with IPF within 5 years prior to Screening, confirmed using ATS/ERS/JRS/ALAT statement for the diagnosis of IPF in effect at the time of this trial's initiation.

- a. Interpretation of HRCT and, if performed, SLB must be confirmed by central over-reader (see [Section 7.1.10.1](#) and [Section 7.1.10.2](#)).
  - b. HRCT performed within 12 months prior to the initiation of Screening that is determined to be of suitable quality by the central over-reader will be used to confirm subject eligibility.
4. SpO2 ≥90% at rest by pulse oximetry while breathing ambient air.
  5. FVC ≥50% of predicted.
  6. FEV1 ≥50% of predicted.
  7. Ratio of FEV1 to FVC ≥0.7.
  8. DLCO corrected for hemoglobin 30% to 79% of predicted, inclusive.
  9. Life expectancy of at least 12 months.

#### 4.2. Exclusion Criteria

Subjects will be excluded from the study if they satisfy any of the following criteria on or before Day 1, as applicable:

1. Serious or uncontrolled medical, surgical, or psychiatric disease that in the opinion of the Investigator would compromise subject safety.
2. History of acute exacerbation of IPF or respiratory tract infection within 3 months prior to Screening.
3. Planned surgery during the study (Day 1 to Additional Follow-up Visit).
4. History of malignant tumor within 5 years prior to Screening (with the exception of treated squamous and basal cell skin cancers and treated Stage 0/*in situ* cervical cancer).
5. History of emphysema or clinically significant respiratory diseases (other than IPF), as determined by the Investigator.
6. History of significant hypersensitivity, intolerance, or allergy to any drug compound, food, or other substance, unless approved by the Investigator.
7. Pregnant or planning to become pregnant during enrollment.
8. Breastfeeding or planning to breastfeed during enrollment.
9. History of alcoholism or drug/chemical abuse within 2 years prior to Day 1.
10. Alcohol consumption >21 units per week for males and >14 units per week for females within 30 days prior to Screening. One unit of alcohol equals 12 oz (360 mL) beer, 1½ oz (45 mL) liquor, or 5 oz (150 mL) wine. Eligible subjects must have agreed not to exceed this limit until the end of the subject's enrollment.
11. Positive urine drugs of abuse at Screening for substance or metabolite of substance that was not prescribed and that remains positive on repeat testing.
12. Positive hepatitis panel (positive for either hepatitis B surface antigen, hepatitis B core antibody, or hepatitis C antibody) and/or positive human immunodeficiency

virus test. Subjects whose results are compatible with prior immunization and not infection may be included at the discretion of the Investigator.

13. Participation in a clinical study involving administration of an investigational drug within 30 days or 5 half-lives, whichever is longer, prior to Day 1.
14. Use or intend to use any medications/products known to alter TRK-250 absorption, metabolism, or elimination processes within 30 days prior to Day 1 and for the remainder of enrollment, unless deemed acceptable by the Investigator.
15. Use or intend to use any nonprescription medications/products including vitamins, minerals, and phytotherapeutic/herbal/plant-derived preparations within 7 days prior to Day 1 and for the remainder of enrollment, unless deemed acceptable by the Investigator.
16. Consumption in any form of tobacco- or nicotine-containing products, excluding over-the-counter or prescription nicotine replacement products approved for marketing by the FDA, within 3 months prior to Day 1.
17. Receipt of blood products within 3 months prior to Day 1.
18. Donation of blood, plasma, or platelets within 6 weeks prior to Day 1.
19. Unable to perform spirometry or to inhale study drug properly, in the opinion of the Investigator. In particular, subjects whose cough may impede proper study treatment, in the opinion of the Investigator, should be excluded.
20. Poor peripheral venous access.
21. Have previously received TRK-250.
22. A subject who, in the opinion of the Investigator, should not participate in this study.
23. Findings that are diagnostic of an alternative condition other than UIP on surgical lung biopsy, HRCT imaging, transbronchial lung biopsy, or BAL.
24. Other known causes of interstitial lung disease (eg, drug toxicities, environmental exposures, connective tissue diseases).
25. End-stage fibrotic disease expected to require organ transplantation within 6 months.
26. Taking a systemic corticosteroid, cytotoxic therapy (eg, chlorambucil, azathioprine, cyclophosphamide, or methotrexate), vasodilator therapy for pulmonary hypertension (eg, bosentan), or unapproved treatment for IPF (eg, interferon-gamma, penicillamine, cyclosporine, mycophenolate, or N-acetylcysteine) within 4 weeks prior to Screening.
  - a. Treatment with pirfenidone (Esbriet®) or nintedanib (Ofev®), though not both concurrently, is permitted, provided that the subject has been on a stable dose for at least 4 weeks prior to Screening and it is anticipated the dose will remain unchanged throughout enrollment (ie, from signing the ICF to the last protocol-specified assessment, whether scheduled or unscheduled).
27. Has received an investigational therapy within 5 half-lives of the agent or 6 months prior to Screening, whichever is longer.

### 4.3. Subject Number and Identification

Subjects will be assigned a subject number prior to the first dosing occasion at the time of their randomization. Assignment of subject numbers will be in ascending order.

Subjects will be identified by subject number only on all study documentation. A list identifying the subjects by subject number will be kept in the Site Master File.

### 4.4. Subject Withdrawal and Replacement

A subject is free to withdraw from the study at any time. In addition, a subject will be withdrawn if any of the following criteria are met:

- change in compliance with any inclusion/exclusion criterion post randomization that is clinically relevant and affects subject safety as determined by the Investigator.
- noncompliance with the study restrictions that might affect subject safety or study assessments/objectives, as considered applicable by the Investigator.
- any clinically relevant sign or symptom that, in the opinion of the Investigator, warrants subject withdrawal.

If a subject is withdrawn, the Sponsor and [REDACTED] will be notified by the Investigator and the date and reason(s) for the withdrawal will be documented in the subject's Case Report Form (CRF). If a subject is withdrawn, efforts will be made to perform all follow-up assessments, including the Additional Follow-up visit assessments, if possible ([Appendix 5](#)). Other procedures may be performed at the Investigator's or Sponsor's discretion. If the subject is in-house, the Safety Follow-up procedures should be performed before the subject is discharged from the clinic, if possible. The Investigator may also request that the subject return for a separate follow-up visit to complete the Safety Follow-up procedures. Any withdrawn subject who completes the Safety Follow-up procedures should be invited to attend for a separate follow-up visit to complete the procedures scheduled for the Additional Follow-up visit; this additional visit should be performed approximately 1 week after the Safety Follow-up procedures. All withdrawn subjects will be followed until resolution of all their AE or until the unresolved AE are judged by the Investigator to have stabilized.

Subjects who are withdrawn for reasons not related to study drug, including randomized subjects who never receive study drug, may be replaced following discussion between the Investigator and the Sponsor to ensure the required number of subjects complete each cohort. Subjects withdrawn as a result of an AE thought to be related to the study drug will generally not be replaced.

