### 3.1. Overall Study Design and Plan

#### 3.1.1. Part A

Part A will comprise a single-dose, single-period, sequential-cohort study. Potential subjects will be screened to assess their eligibility to enter the study within 28 days prior to study drug administration.

The total duration of study participation for each subject (from Screening through Additional Follow-up visit) is planned to be no more than 7 weeks but may be increased to a maximum

of 9 weeks if the Additional Follow-up visit is delayed based on findings from the ongoing review of data by the data monitoring committee (DMC).

It is planned that 16 subjects will be studied in 4 cohorts (Cohorts A1 to A4), each consisting of 4 subjects. Following DMC review of the safety and tolerability data from the first 4 cohorts, up to 3 further optional cohorts (Cohorts A5 to A7) of at least 4 subjects may be added to Part A to evaluate additional doses or to further evaluate planned doses.

[REDACTED]

[REDACTED]

All subjects will return for a Safety Follow-up visit 7 (+3) days after dosing and an Additional Follow-up visit 14 ( $\pm 3$ ) days after dosing. The timing of the Additional Follow-up visit for a cohort may be changed to a maximum of 28 ( $\pm 3$ ) days after dosing, based on emerging safety data.

In each of Cohorts A1 to A4, 3 subjects will receive TRK-250 and 1 subject will receive placebo. All doses will be administered in accordance with a randomization schedule on the morning of Day 1. Each subject will receive only a single dose of TRK-250 or placebo during the study. [REDACTED]

[REDACTED]

[figure not shown]
- Cohort A1: 2 mg
- Cohort A2: 10 mg
- Cohort A3: 30 mg
- Cohort A4: 60 mg

[REDACTED]

[REDACTED] pharmacologically active dose levels (ie, when the escalated dose will be  $\geq 34.7$  mg).

An overview of the study design and the planned dose levels are shown in [Figure 1](#).

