10 STATISTICAL METHODOLOGY

10.1 General

Data listings will be provided for the All Subjects Population. Summary statistics and statistical analyses will be performed for subjects included in the relevant analysis populations

For continuous data, summary statistics will include the arithmetic mean, arithmetic standard deviation, median, minimum, maximum, and number. For log-normal data (eg, the PK parameters: areas under the concentration-time curve [AUCs] and maximum observed concentration [C_{max}]), the geometric mean and geometric coefficient of variation (CV%) will also be presented. For categorical data, frequency counts and percentages will be presented. Data listings will be provided for all subjects up to the point of withdrawal, with any subjects excluded from the relevant population highlighted. For the calculation of summary statistics and statistical analysis, unrounded data will be used.

Missing values will not be imputed.

Data analysis will be performed using SAS[®] Version 9.4 or greater.

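### Protocol 4.4 sets no last-dose anchor for withdrawn subjects' follow-up, so an in-house Part A withdrawal may be last seen at about 7–8 days instead of 14; SAP 10.1 also cuts listings at withdrawal

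*Protocol*

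**What the plan says.** For Part A, protocol 3.1.1 states: "All subjects will return for a Safety Follow-up visit 7 (+3) days after dosing and an Additional Follow-up visit 14" (±3) days after dosing. For Part B, 3.1.2 states: "All subjects will return for a Safety Follow-up visit approximately 7 days after their last dose", given as Day 29 (+3), with "an Additional Follow-up visit approximately 14 days after the last dose (Day 36" (±3). In both parts the second visit can be postponed for a cohort on emerging safety data; in Part B it "may be changed to a maximum of approximately 28 days after the last dose (Day 50" (±3).

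Section 4.4 covers withdrawn subjects. It asks for efforts to complete all follow-up assessments and points to Appendix 5. It then adds: "If the subject is in-house, the Safety Follow-up procedures should be performed before the subject is discharged from the clinic, if possible". A separate return for those procedures is something the Investigator may request. Whoever completes them should be invited for the Additional Follow-up, and "this additional visit should be performed approximately 1 week after the Safety Follow-up procedures". The section mentions neither the date of the last dose nor a cohort extension.

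In Appendix 5, ECG, clinical chemistry, hematology and body weight are scheduled at Safety Follow-up but not at Additional Follow-up.

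SAP 10.1 states: "Data listings will be provided for all subjects up to the point of withdrawal". SAP 10.6.1 provides for every AE to be listed and gives no cut-off.

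**The concern.** This is a first-in-human trial with safety as its primary objective. ECG parameters, laboratory results and body weight are among the primary endpoints, and Safety Follow-up is the last scheduled occasion for all three. If those procedures are done before an early discharge, the final scheduled values describe the first hours after dosing, not the first week. The last visit, which includes spirometry and DLCO, moves forward with them. A late effect in that subject could be missed, and the subject's follow-up values would not be comparable with those of subjects who complete.

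The analysis plan adds two problems. Safety analysis is descriptive only, so the listings carry much of the evidence, and the SAP's listing rule read literally leaves out assessments that 4.4 asks sites to collect. SAP 10.1.2 also keeps results taken off schedule out of summaries, except as baseline. The SAP does not say whether an early set of Safety Follow-up laboratory tests would be pooled with other subjects' Day 7–10 values or treated as unscheduled and dropped.

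**Working it through.** No sample-size calculation bears on this; the check is day arithmetic.

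**1. The plan's own intervals (3.1.2).** The last Part B dose is on Day 22. Safety Follow-up: 29 − 22 = 7 days. Additional Follow-up: 36 − 22 = 14 days. Latest extension: 50 − 22 = 28 days. All three match the stated figures. The gap between the two visits is 14 − 7 = 7 days, or 36 − 29 = 7 days. In an extended cohort it becomes 28 − 7 = 21 days (50 − 29 = 21).

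**2. Withdrawn subjects under 4.4.** Let *w* be the days from the last dose to the Safety Follow-up procedures. The Additional visit then falls at *w* + 7. The documents do not give *w*, so it is shown as an assumed range of 0 to 7 days:

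| *w* | Last visit (*w* + 7) | Share of 14 days | Share of 28 days |
|---|---|---|---|
| 0 | 7 | 50% | 25% |
| 1 | 8 | 57% | 29% |
| 3 | 10 | 71% | 36% |
| 5 | 12 | 86% | 43% |
| 7 | 14 | 100% | 50% |

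**3. Which values of *w* the text makes possible.** The Synopsis keeps the first two subjects of each Part A cohort on site from Day 1 to Day 2. Withdrawal during that stay gives *w* = 0 or 1 (2 − 1 = 1). Final scheduled ECG and laboratory tests then fall 0–1 days after dosing, against 7–10 for other subjects. The last visit falls at about 7–8 days, against 14 (window 11–17). Over that window the share runs from 7/17 = 41% to 8/11 = 73%.

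**4. What drives the shortfall.** In an unextended cohort, the one-week gap in 4.4 equals the gap completers have, so any shortfall comes from doing the Safety procedures early and is 7 − *w* days. In a cohort extended to 28 days, the one-week gap itself falls short of the 21-day gap. For *w* = 0–7 the last visit is at 7–14 days, or 25–50% of 28.

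**5. The Appendix 5 pointer.** If Study Days 29 and 36 are applied literally in Part B, the two visits fall this long after the last dose:

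- last dose Day 1: 29 − 1 = 28 and 36 − 1 = 35 days
- last dose Day 8: 21 and 28 days
- last dose Day 15: 14 and 21 days
- last dose Day 22: 7 and 14 days

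A Part B subject who stops after the first dose is thus last seen at about 14 days under 3.1.2, at 35 days under Appendix 5, and at *w* + 7 days under 4.4.

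**6. Listings.** Protocol 4.4 seeks assessments after withdrawal, SAP 10.1 ends listings at withdrawal without defining that point, and SAP 10.6.1 lists all AEs. The three cannot all be followed literally for a withdrawn subject who attends follow-up.

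**The case against.** The best defence is that 4.4 opens with a general instruction to complete all follow-up assessments and refers to the schedule. Only its in-house sentence brings the Safety procedures forward, qualified by feasibility, and examining someone before they leave secures data from a subject who may not return. Other provisions also help. Withdrawn subjects' AEs are followed until they resolve or stabilize. Sections 7.1.2 and 7.1.4 provide for extra laboratory tests and ECGs when clinically appropriate. Appendix 1 asks for notification of possibly related SAEs after a subject has left. Withdrawals include free choice and noncompliance, so withdrawn subjects need not be those who reacted to the drug. On the SAP, 10.1 also provides listings for the All Subjects Population and states no withdrawal cut-off for summaries.

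Much of this stands, and it limits the point to a gap in wording. It does not remove the gap. The general instruction sets no timing, and its pointer leads to study days that conflict with 3.1.2 for early stoppers. AE follow-up covers events already known, SAE notification depends on the investigator becoming aware of the event, and discretionary tests are not scheduled ones. None of these fixes a later ECG, laboratory panel, spirometry or DLCO. The All Subjects sentence does not override the cut-off that follows it in the same section.

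**Conclusion.** The protocol gives no single timing rule for withdrawn subjects. In the clearest case, a Part A subject withdrawn in-house on Day 1 or 2, the last scheduled ECG and laboratory tests may fall 0–1 days after dosing and the last visit at about 7–8 days instead of 14. That is a shortfall of 6–7 days, and a larger one if the cohort is extended to 28. It rests on the pre-discharge procedures counting as the Safety Follow-up visit, which 4.4 implies but does not state. One such subject would be 1 of 3 on active drug in a Part A cohort (33%). No withdrawal rate is given, so how often this would happen is unknown.

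A reader might go further and infer that 4.4 times visits from withdrawal, or that subjects who stop early generally get half the follow-up. The documents do not support either reading. The text ties the Safety procedures to discharge for in-house subjects only and is otherwise silent on timing. Half is the *w* = 0 end of the range in an unextended cohort; a subject whose Safety procedures fall 7 days after the dose has no shortfall there. Extending the example to Part B would require a residential stay, and no visible text provides one; parts of that design text are redacted.

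The SAP conflict is separate and does not depend on these assumptions. It is confined to listings.

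**What to change.** Protocol: reconcile 4.4 with 3.1.1, 3.1.2 and Appendix 5 so that one timing rule applies to withdrawn subjects. The rule should cover what happens when a cohort's Additional Follow-up has been postponed, and should say whether procedures done before discharge replace the Safety Follow-up visit or are additional to it. Which schedule to adopt is for the sponsor and investigators to decide.

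SAP 10.1: replace the withdrawal cut-off with wording that lists all data collected, including follow-up assessments made after withdrawal, in line with protocol 4.4 and SAP 10.6.1. State as well how Safety Follow-up results obtained early are assigned to a timepoint under SAP 10.1.2.

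The cost is wording in both documents and, depending on the rule adopted, at most one extra outpatient visit for a withdrawn subject who agrees to attend. The SAP change requires no new data.
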